**Table 1. Primary and secondary research questions and objective.**

#### **A. Primary research question and objective.**

Objective:	
Objective 1: To measure the incidence of diagnosed ILD in four European countries, overall and stratified by age, sex and calendar time. This analysis will be repeated for the following ILD subtypes: alveolitis/pneumonitis (excluding aspiration and infectious pneumonitis), lung fibrosis and drug induced ILD).
 
Objective 2: To describe the characteristics of patients diagnosed with ILD in four European countries in terms of demographics (age and sex), comorbidities, and medications used in the one year prior to diagnosis. This analysis will be repeated for the following ILD subtypes: alveolitis/pneumonitis (excluding aspiration and infectious pneumonitis), lung fibrosis and drug induced ILD).
 
Objective 3: To measure survival rates in patients diagnosed with ILD in four European countries overall and stratified by age, sex and calendar time. This analysis will be repeated for the following ILD subtypes: alveolitis/pneumonitis (excluding aspiration and infectious pneumonitis), lung fibrosis and drug induced ILD).

Hypothesis:	Not applicable
Population (mention key inclusion-exclusion criteria):	All patients should be present in the databases with at least 365 days of prior history (except for CDWBordeaux) and be newly diagnosed with ILD (i.e. no prior diagnosis of ILD).
Exposure:	None

	D2.2.3 - Study Protocol for P3-C1-005	
	Author(s): [name] [name]	Version: V2.1
	Dissemination level: Public	

Comparator:	None
Outcome:	Overall survival (objective 3)
Time (when follow up begins and ends):	Follow-up starts after study start date (1st January 2010) or on the date where there is 1 year of prior history. (one year of history not needed for CDWBordeaux) whatever comes last. For objective 2 and 3, the follow-up starts upon the first diagnosis of ILD. The End of follow-up will be defined as the earliest of loss to follow-up, end of data availability, death, or end of study period (31st of December 2022), whatever comes first.
Setting:	Primary care data (CPRD GOLD, BIFAP, IQVIA DA Germany) and secondary care data (CDW Bordeaux).

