### Patient-level characterisation

The study cohort will include all individuals registered in the database between 1st of January 2010 and 31st of December 2022, with at least 365 days of data visibility (except for CDWBordeaux) and a new ILD diagnosis.

The concept definition of ILD and ILD-subtypes is described in Table S1, [Appendix I](#). The operational definitions of the inclusion and exclusion criteria are presented by means of [Table 5](#) and [Table 6](#), respectively.

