**Table 5. Operational Definitions of Inclusion Criteria.**

Criterion	Details	Order of application	Assessment window	Care Settings 	Code Type	Diagnosis position 	Applied to study populations:
Observation period in the database during the period 2010-2022 (or the latest date available)	All individuals present in the period 2010-2022 (or the latest date available)	After	n/a	IP, OP, OT	n/a	n/a	All individuals within selected databases
Prior database history	Study participants will be required to have 365 days of prior history observed before contributing observation time	Prior	[-365, -1]	OP	n/a	n/a	All individuals within CPRD GOLD, BIFAP and IQVIA DA Germany
Washout period	Individuals newly diagnosed with ILD will be required not to have a diagnosis of ILD any time prior to the diagnosis of ILD	Prior	[-inf, -1]	OP	n/a	n/a	All individuals diagnosed with ILD

 IP = inpatient, OP = outpatient, ED = emergency department, OT = other, n/a = not applicable

 Specify whether a diagnosis code is required to be in the primary position (main reason for encounter)

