#### Covariates for the patient-level characterisation study

As part of patient-level characterisation study, comorbidities will be measured in the period of 365 days prior to the index date (i.e. date of diagnosis of ILD). Concomitant medications will be measured within 30 and 365 days prior to the index date and reported for both time periods.

Covariates used to describe Patient characterisation consist of the following:

- Sex
- Age at index date (i.e. date of diagnosis of ILD). Age will be presented in age categories namely:
  - <18
  - 18-39
  - 40-59
  - 60-79
  - >=80 years.
- ILD subtypes:
  - alveolitis/pneumonitis (excluding aspiration and infectious pneumonitis)
  - lung fibrosis
  - drug-induced

	D2.2.3 - Study Protocol for P3-C1-005	
	Author(s): [name] [name]	Version: V2.1
	Dissemination level: Public	

- Unspecified ILD
- description of the top 10 of the most frequent comorbidities and concomitant medications using large-scale characterisation, as specified in the CohortCharacteristics R package and assessed in the period of 365 days prior to the index date.
- Comorbidities of interest (Gaillet, Favelle et al. 2015, Choi, Dauti et al. 2018, Joy, Arbiv et al. 2023), in particular:
  - COPD/emphysema
  - Connective tissue disease namely rheumatoid arthritis, sclerodermia, systemic lupus erythematosus (SLE), polymyositis/dermatomyositis, granulomatosis with polyangiitis (GPA)
  - GERD
  - Hepatitis B/C
  - Cancer excluding non-melanoma skin cancer
- Use of concomitant medication (assessed in the 30 days and 365 days prior to the index date) in particular:
  - chemotherapy
  - amiodarone
  - immune checkpoint inhibitors (ICIs)
  - tyrosine kinase inhibitors (TKIs including crizotinib, EGFR inhibitors, erlotinib, gefitinib)
  - mammalian target rapamycin (mTOR) inhibitors
  - rituximab
  - statins
  - methotrexate
  - nitrofurantoin
  - tumor necrosis factor (TNF)- $\alpha$  antagonists (Paolo, Philippe et al. 2022).

The operational definition of the covariates is described in [Table 7](#). Index date is the start of the incident ILD diagnosis during the study period. The preliminary concepts for prespecified conditions and drugs of interest are described in [Appendix I](#).

	D2.2.3 - Study Protocol for P3-C1-005	
	Author(s): [name] [name]	Version: V2.1
	Dissemination level: Public	

**Table 7.** Operational Definitions of Covariates.

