### 8.8.3 Statistical model specification and assumptions of the analytical approach considered

*Objective 1. Incidence of Diagnosed ILD and Common Subtypes:* Calculation of population-based incidence rates is part of our pipelines for population-level descriptive epidemiology. This analysis will be performed using the *IncidencePrevalence* R package and will provide overall incidence rates, stratified by age, sex, and calendar year. (Ed 2024) Additionally, it can be repeated for prespecified ILD subtypes (alveolitis/pneumonitis (excluding aspiration and infectious pneumonitis), lung fibrosis and drug induced ILD). To ensure the reliable estimation of incidence rate of ILD using an appropriate denominator population, this objective will be investigated within the primary care databases: BIFAP, CPRD GOLD, and IQVIA DA Germany.

	D2.2.3 - Study Protocol for P3-C1-005	
	Author(s): [name] [name]	Version: V2.1
	Dissemination level: Public	

*Objective 2. Characterization of Patients Diagnosed with ILD:* Description of patient characteristics is part of our pipelines for patient-level characterisation. Characterization of patient demographics, comorbidities, risk factors, and treatments before diagnosis, as well as characterizing common ILD subtypes at diagnosis, will be conducted using the *CohortCharacteristics* and *CohortDiagnostics* R packages. (Marti 2024) This objective can be explored in all participating databases.

*Objective 3. Survival Rates in Patients Diagnosed with ILD:* Estimation of survival rates is part of our pipelines for patient-level characterisation. *CohortSurvival* R package can estimate survival rates stratified by age, sex, and year. Analysis can be repeated for the prespecified ILD subtypes, subject to sufficient data availability. (Ed 2024) This objective will be investigated in databases with complete mortality data such as BIFAP, CPRD GOLD and CDWBordeaux.

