### **8.8.6 Methods to deal with missing data**

For the disease epidemiology studies we assume that the absence of a diagnosis record means that the person did not receive the diagnosis.

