10.6 Does the plan describe methods for analytic control of outcome misclassification?				

	D2.2.3 - Study Protocol for P3-C1-005	
	Author(s): [name], [name]	Version: V2.1
	Dissemination level: Public	

Section 10: Analysis plan	Yes	No	N/A	Section Number
10.7 Does the plan describe methods for handling missing data?				
10.8 Are relevant sensitivity analyses described?				8.8

Comments:

--

Section 11: Data management and quality control	Yes	No	N/A	Section Number
11.1 Does the protocol provide information on data storage? (e.g., software and IT environment, database maintenance and anti-fraud protection, archiving)				9.2
11.2 Are methods of quality assurance described?				10.0
11.3 Is there a system in place for independent review of study results?				

Comments:

--

Section 12: Limitations	Yes	No	N/A	Section Number
12.1 Does the protocol discuss the impact on the study results of: 12.1.1 Selection bias? 12.1.2 Information bias? 12.1.3 Residual/unmeasured confounding? (e.g., anticipated direction and magnitude of such biases, validation sub-study, use of validation and external data, analytical methods).	  	  	  	11
12.2 Does the protocol discuss study feasibility? (e.g. study size, anticipated exposure uptake, duration of follow-up in a cohort study, patient recruitment, precision of the estimates)				8.2

Comments:

--

Section 13: Ethical/data protection issues	Yes	No	N/A	Section Number

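### CDWBordeaux is exempt from the 365-day history rule, so for patients with little or no earlier hospital record the ILD washout is uninformative and the look-back in objective 2 is unobserved but counted as 'no', and no analysis shows the effect

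*Protocol*

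**What the plan says.** The waiver is stated consistently. Table 1 (section 7, Time row) has "one year of history not needed for CDWBordeaux". That clause concerns when denominator follow-up starts. The operative text for the ILD cohort is in section 8.5, Patient-level characterisation, which includes people "with at least 365 days of data visibility (except for CDWBordeaux) and a new ILD diagnosis". Table 5 matches it, applying the prior-history criterion to "All individuals within CPRD GOLD, BIFAP and IQVIA DA Germany".

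The washout is not waived. Table 5 applies it, over [-inf, -1], to everyone diagnosed with ILD: "Individuals newly diagnosed with ILD will be required not to have a diagnosis of ILD any time prior to the diagnosis of ILD". No minimum observable time stands behind it in CDWBordeaux.

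The look-back is the same in every database. Section 8.6.3 says "comorbidities will be measured in the period of 365 days prior to the index date", with medications over 30 and 365 days. Table 7 makes these binary variables with windows [-365, 0] and [-30, 0], so day 0 is included there. Section 8.8.5 reports the number and percentage with a record in the window.

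On use of the sources, section 8.8.3 says of incidence that "this objective will be investigated within the primary care databases: BIFAP, CPRD GOLD, and IQVIA DA Germany". Objective 2 can use all four databases, and objective 3 uses BIFAP, CPRD GOLD and CDWBordeaux.

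Item 10.8 of the ENCePP checklist (Appendix II) asks "Are relevant sensitivity analyses described" and is ticked Yes with reference to 8.8.

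**The concern.** In the three other databases, 365 days of observation before index give the washout and the look-back something to work on. In CDWBordeaux a patient whose first hospital record is the ILD code passes the washout automatically, whether the disease is new or was diagnosed elsewhere years before. For the same patient nothing before day 0 can be seen, yet the binary variable has no value for 'not observed', so it is reported as 'no'.

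Two results are exposed. In objective 2, percentages with a comorbidity or prior drug are pulled downwards. This matters because section 11 names CDWBordeaux as the exception to the expected under-recording of ILD-related drugs given in hospital, and the study is meant to inform assessment of drug-induced ILD. In objective 3, section 8.1 counts survival from first diagnosis. For a patient referred with existing disease the clock starts at first hospital record: time already lived with ILD is left out, and people who died before reaching the hospital are not in the cohort. The net direction cannot be settled from the protocol.

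**Working it through.** The protocol gives no figure for this point, so there is none to reproduce. The check has two parts.

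**1. Reading the rules together for a first-contact patient in CDWBordeaux**

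| Rule | Place | Consequence |
|---|---|---|
| History requirement | 8.5, Table 5 | Does not apply |
| ILD washout, [-inf, -1] | Table 5 | Passed by default, as there are no earlier records |
| Comorbidity and drug windows | 8.6.3, Table 7 | Days -365 to -1 (and -30 to -1) unobserved; day 0 counts under Table 7 |
| Reporting | 8.8.5 | Percentage with a record; unobserved and absent look alike |
| Sensitivity analysis or restriction | 8.8 | None described |
| Limitation stated | 11 | None on the waiver |

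Section 8.6.3 describes the period as before the index date, while Table 7 includes day 0. I used Table 7, which is the reading more favourable to the plan.

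Section 8.8.6 adds that "the absence of a diagnosis record means that the person did not receive the diagnosis", but it is worded for the disease epidemiology part. The argument therefore rests on Table 7 and 8.8.5.

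**2. Size, as an illustration**

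Inputs:
- *p*, the true 365-day prevalence of a characteristic: assumed 20%.
- *f*, the share of CDWBordeaux patients with no observed look-back: not given, assumed 10% to 60%.
- *d*, the part of the true history of such patients that is coded on day 0: not given, set to 0 as the worst case.
- *N* = 3,900, the feasibility count in section 8.7. It is a rounded count and not the final cohort.
- True prevalence is taken as equal in patients with and without look-back.

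Reported prevalence = *p* × (1 − *f* × (1 − *d*)), which for *d* = 0 is *p* × (1 − *f*). The shortfall is *p* × *f* × (1 − *d*), so it shrinks in proportion to what day 0 captures and vanishes at *d* = 1.

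Sampling error for comparison: 1.96 × √(0.20 × 0.80 / 3,900) = 1.26 percentage points.

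| *f* | Reported | Shortfall (points) | Patients with look-back | 95% half-width in them (points) |
|---|---|---|---|---|
| 10% | 20 × 0.90 = 18% | 2 | 3,510 | 1.32 |
| 30% | 20 × 0.70 = 14% | 6 | 2,730 | 1.50 |
| 50% | 20 × 0.50 = 10% | 10 | 1,950 | 1.78 |
| 60% | 20 × 0.40 = 8% | 12 | 1,560 | 1.98 |

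The last column is 1.96 × √(0.16 / *n*) with *n* = 3,900 × (1 − *f*).

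The shortfall equals the sampling error when *f* = 1.26 / 20 = about 6%. The same calculation gives about 14% for *p* = 5%, 9% for *p* = 10% and 5% for *p* = 30%. With no day-0 capture, a modest share of first-contact patients is therefore enough for this bias to exceed the random error in the Bordeaux percentages.

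**The case against.** The strongest reply is that the waiver is a disclosed and consistent choice, reasonable for a hospital source, and that a restricted analysis is ordinary SAP content. The first half stands: the waiver is not an error and need not be withdrawn. The second half is weaker here. Section 5 mentions an SAP only as something that might be requested, 8.8.4 says all methods are predefined through the packages in 8.8.3, and the checklist points to 8.8 for sensitivity analyses that are not there.

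Several stronger readings are tempting, and the documents do not support them:

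- *That no CDWBordeaux patient is shown to be newly diagnosed.* Data collection began in 2005, so patients with earlier hospital contact do have a real washout.
- *That the look-back is empty.* Table 7 counts day 0, and the warehouse holds billing-coded conditions, outpatient prescriptions and inpatient orders and administrations. Only days -365 to -1 are unobserved.
- *That incidence is biased, because the Table 1 clause concerns denominator follow-up.* CDWBordeaux is not used for objective 1.
- *That the affected share is known to be large.* Nothing in the protocol fixes it; even the 10% to 60% range is an assumption.

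Other points also stand. Databases are reported separately without meta-analysis (8.9), so the harm is to Bordeaux's own figures and to side-by-side reading. Index dates in primary care may also be imperfect, since section 11 notes that ILD is diagnosed by specialists. The checklist mismatch is general and promises nothing specific to CDWBordeaux.

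**Conclusion.** The concern holds for objectives 2 and 3 in CDWBordeaux, for patients with little or no earlier hospital record. For them the washout does not separate new from existing ILD, unobserved history before day 0 is counted as absent, and survival may start at first hospital contact.

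On the assumptions above, a true 20% would be reported as 18% if 10% of patients are affected and as 8% if 60% are. These are worst-case values with no day-0 capture; with full capture the shortfall is nil. No size or direction is claimed for survival. The plan should be changed so that the affected share is measured and its effect shown. The waiver itself can stay.

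**What to change.** 1. Keep the full CDWBordeaux cohort as the main analysis.
2. Report, for CDWBordeaux, the distribution of time from first warehouse record to index and the share of patients with at least one record in [-365, -1].
3. Name in 8.8.5 a sensitivity analysis that repeats objectives 2 and 3 among CDWBordeaux patients with at least 365 days since first record **and** at least one record in [-365, -1]. The first condition alone is not enough: a patient with a single visit three years earlier would meet it and still have an unobserved year before index.
4. State beside the results that this subgroup selects patients with more prior hospital contact, so a difference from the full cohort mixes look-back completeness with case mix.
5. Add the waiver and its consequences to section 11. With step 3 in place, the Yes at checklist item 10.8 becomes correct.
6. Align 8.6.3 and Table 7 on whether day 0 belongs to the look-back.

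The cost is one additional run in one database and a few sentences. The subgroup is less precise, but at *p* = 20% the half-width rises only from 1.26 to between 1.32 and 1.98 points over the assumed range, if the share excluded equals *f*.

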## 8. RESEARCH METHODS

### 8.1 Study type and Study Design

The Study Types with related Study Designs are described in the **Table 2** below and are selected from the Catalogue of Data analytics.

A cohort study will be conducted using routinely collected health data from four databases. The study will comprise two consecutive parts:

- To address objective 1: A population-based cohort study including newly diagnosed ILD and ILD-subtype patients, to assess the incidence rates of ILD, stratified by different age categories, sex and calendar date. The denominator population includes all present in the database with at least one year of data availability (not for CDWBordeaux).
- To address objective 2: A cohort of newly-diagnosed ILD patients to characterise them with regards to the most common comorbidities, concomitant medications, age at first diagnosis, sex and calendar year. This analysis will be done in the overall group of individuals newly diagnosed with ILD and by ILD subtypes (see above).

	D2.2.3 - Study Protocol for P3-C1-005	
	Author(s): [name] [name]	Version: V2.1
	Dissemination level: Public	

- To address objective 3: A cohort of newly-diagnosed ILD and ILD subtype patients to calculate survival time from the date of first diagnosis of ILD to date of death, stratified by age category (at first diagnosis), sex and calendar date (year at index date).

**Table 2.** Description of Potential Study Types and Related Study Designs.

STUDY TYPE	STUDY DESIGN	STUDY CLASSIFICATION
Population-level descriptive epidemiology	Population-level cohort	Off the shelf (C1)
Patient-level characterisation	Cohort analysis	Off the shelf (C1)

## 8.2 Study Setting and Data Sources

This study will be conducted using routinely collected data from four databases in four European countries. All databases were previously mapped to the OMOP Common Data Model (CDM).

1. Clinical Practice Research Datalink (CPRD) GOLD, United Kingdom
2. Base de datos para la Investigacion Farmacoepidemiologica en el Ambito Publico (BIFAP), Spain
3. Clinical Data Warehouse (CDW) Bordeaux, France
4. IQVIA Disease Analyzer Germany (IQVIA DA Germany), Germany

For this study, four databases in the DARWIN EU® Database Catalogue were considered fit for purpose. The selection process was based on the size of the databases, the number of individuals with the diagnosis of interest, the suitability of denominator population for population-level rates, information regarding mortality, geographical spread and the experience gained from databases that participated in other similar DARWIN EU® studies. Based on the feasibility assessment performed, the suggested databases are considered fit for purpose for at least part of the objectives.

Information on data sources planned to be used with a justification for their choice in terms of ability to capture the relevant data is described in [Table 3](#).

When it comes to assessing the reliability of data sources, the data partners are asked to describe their internal data quality process on the source data as part of the DARWIN EU® onboarding procedure. To further ensure data quality, we utilize the Achilles tool, which systematically characterizes the data and generates data characteristics such as age distribution, condition prevalence per year, data density, measurement value distribution can be compared against expectations for the data. Additionally, the data quality dashboard (DQD) provides more objective checks on plausibility consistently across the data sources. In terms of relevance, more general-purpose diagnostic tools, CohortDiagnostics and DrugExposureDiagnostics, were developed. The CohortDiagnostics package provides additional insights into cohort characteristics, record counts and index event misclassification. The DrugExposureDiagnostics package assesses ingredient specific diagnostics for drug exposure records. Furthermore, data is maintained up to date by extracting the release dates for each dataset in the network and monitoring when data are out-of-date with the expected refresh cycle (typically quarterly or half-yearly). In addition, it is important to have clear understanding of the time period covered by each released database, as this can vary across different domains. To facilitate this, the CDMOnboarding (and Achilles) packages contain a 'data density' plot. This plot displays the number of records per OMOP domain on a monthly basis. This

	D2.2.3 - Study Protocol for P3-C1-005	
	Author(s): [name] [name]	Version: V2.1
	Dissemination level: Public	

allows to get insights when data collection started, when new sources of data were added and when until when data was included.

**Table 3.** Description of the selected Data Sources.

Country	Name of Database	Justification for Inclusion	Health Care setting	Type of Data	Number of active subjects	Feasibility count of disease (ILD)*	Data lock for the last update
United Kingdom	CPRD GOLD	
Adequate number of individuals with the diagnosis of interest,
 
Suitable denominator population for population-level rates,
 
Adequate information regarding mortality is captured
 
Contribute to geographical diversity of data sources included
	Primary care	EHR	17m	6,900	04/11/2023
Spain	BIFAP	
Adequate number of individuals with the diagnosis of interest
 
Suitable denominator population for population-level rates
 
Adequate information regarding mortality is captured
	Primary care	EHR	22m	7,900	31/03/2023

Country	Name of Database	Justification for Inclusion	Health Care setting	Type of Data	Number of active subjects	Feasibility count of disease (ILD)*	Data lock for the last update
		Contribute to geographical diversity of data sources included					
France	CDW Bordeaux	
Adequate number of individuals with the diagnosis of interest
 
Adequate information regarding mortality is captured
 
Contribute to geographical diversity of data sources included
	Secondary care	EHR	2.4m	3,900	16/11/2023
Germany	IQVIA DA Germany	
Adequate number of individuals with the diagnosis of interest
 
Suitable denominator population for population-level rates
 
Contribute to geographical diversity of data sources included
	Primary care and outpatient secondary care	Claims	43m	8,800	23/01/2024

\*Counts for ILD overall (not for the different subtypes). The feasibility assessment with counts for the different conceptids has been added in the appendix. Rounded up to the nearest hundred.

Clinical Practice Research Datalink GOLD, United Kingdom (University of Oxford)

	D2.2.3 - Study Protocol for P3-C1-005	
	Author(s): [name] [name]	Version: V2.1
	Dissemination level: Public	

The Clinical Practice Research Datalink (CPRD) GOLD is a database of anonymised electronic health records (EHR) from General Practitioner (GP) clinics in the UK that use the Vision® software system for their management.(Herrett, Gallagher et al. 2015) The source population encompasses 98% of the UK, registered with GPs responsible for non-emergency care and referrals. Participating GPs provide CPRD EHR for all registered patients who did not specifically request to opt out of data sharing. Covering 4.6% of the current UK population, GOLD includes 4.9% of contributing GP practices, providing comprehensive information within its defined source population. GOLD contains data from all four UK constituent countries and the current regional distribution of its GP practices is 5.7% in England, 55.6% in Scotland, 28.4% in Wales, and 10.2% in Northern Ireland (May 2022).

GOLD data include patient’s demographic, biological measurements, clinical symptoms and diagnoses, referrals to specialist/hospital and their outcome, laboratory tests/results, and prescribed medications. GOLD has been assessed and found broadly representative of the UK general population in terms of age, gender, and ethnicity.(Herrett, Gallagher et al. 2015) GOLD has been widely used internationally for observational research to produce nearly 3,000 peer-reviewed publications, making GOLD the most influential UK clinical database so far.(Carey, Nirmalanathan et al. 2023, Fahmi, Wong et al. 2023, Wigglesworth S 2023).

In terms of quality checks, the integrity, structure and format of the data is reviewed. Collection-level validation ensures integrity by checking that data received from practices contain only expected data files and ensures that all data elements are of the correct type, length and format. Duplicate records are identified and removed. Transformation-level validation checks for referential integrity between records ensure that there are no orphan records included in the database (for example, that all event records link to a patient), while research-quality-level validation covers the actual content of the data. CPRD provides a patient-level data quality metric in the form of a binary ‘acceptability’ flag. This is based on recording and internal consistency of key variables including date of birth, practice registration date and transfer out date.

